16.5 Expedited Reporting of Serious Adverse Events

Any Serious Adverse Event, and device deficiencies should be reported to Vibrant Ltd. within 24 hours of investigators' knowledge of the event. Investigator should report these events on the appropriate SAE form / Device Deficiencies Form in the eCRF and send the form by fax or e-mail, to the following safety contact person:

If applicable, the investigator should also inform the representative of the appropriate local Ethics Committee, within 24 hours of investigator's awareness of the event. A copy of the report cover letter should be filed within the study file.

The sponsor is responsible for the ongoing safety evaluation of the investigational medical device. The sponsor will promptly notify all concerned investigator(s)/institution(s) and the regulatory authority(ies) of findings that could affect adversely the safety of subjects, impact the conduct of the trial, or alter the Medical Ethics Committee approval/favorable opinion to continue the trial.

The sponsor will expedite the reporting to all concerned investigator(s)/institutions(s), to the EC(s), where required, and to the regulatory authority(ies) of the occurrence of Unanticipated Serious Adverse Device Effects.

16.6 Sponsor's Reporting to National Competent Authorities (NCA)

The sponsor of the clinical investigation (which could be the manufacturer (MFR), or his authorized representative (AR)) have to report at the same time to all NCAs where the clinical investigation has commenced, the following reportable events:

1. Any SAE

Doc No: 220CLD

Rev: 03 Date: August 26, 2016

Page 54 of 93

2. Any Investigational Medical Device Deficiency that might have led to a SAE if

- a) suitable action had not been taken OR
- b) intervention had not been made OR
- c) if circumstances had been less fortunate
- 3. New findings/updates in relation to already reported events.
- A SAE which indicates an imminent risk of death, serious injury, or serious illness and that requires prompt remedial action for other patients/subjects, users or other persons or a new finding to it, should be reported immediately, but not later than 2 calendar days after awareness by sponsor.
- Any other reportable events or a new finding/update to it should be reported immediately, but not later than 7 calendar days following the date of awareness by the sponsor.

Reporting should be made using the SAE reporting guidelines in Title 21 of the Code of Federal Regulations (21 CFR), part 312 (Investigational New Drug Application), Section 32 (IND Safety Reporting) and part 812 (Investigational Device Exemptions), Section 150 (Reports).

Sponsor will also submit to the NCAs all safety updates and periodic reports, as required by applicable regulatory requirements.

16.7 Follow- Up of Unresolved Events

All adverse events should be followed until they are resolved or the subject's participation in the study ends.

17. STATISTICAL CONSIDERATIONS

17.1 Study Design and Objectives

The study is planned as a prospective, multicenter, open-label, single-arm study, designed to assess the tolerability, safety, ease of use and efficacy of active Vibrant capsule when administered 14 times every 3 weeks in patients with Functional Constipation.

After a run-in period of 14 days, subjects will be treated with the active Vibrant capsule

After a run-in period of 14 days, subjects will be treated with the active Vibrant capsule for 6 weeks.

An adaptive design with 1 interim analysis is planned.

17.2 Study Endpoints

17.2.1 Primary Efficacy Endpoint

The primary efficacy endpoint is the SBM success rate, defined as an increase from the run-in period of at least one weekly Spontaneous Bowel Movement (SBM) during at least 3 of the 6 weeks of treatment. Subjects with less than 2 weeks (with at least 5 days per week) of valid diary during the treatment period will be considered as non-evaluable.

Doc No: 220CLD

Rev: 03 Date: August 26, 2016

Page 55 of 93

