	The study will have one interim analysis. The interim analysis will be performed after 20 patients complete the study and are evaluable. The following parameters will be assessed: ease of use of the home base unit, tolerability and safe use of the new frequency of Vibrant Capsule administration.
	Patients will follow a 2 weeks baseline period and then take the Vibrant Capsule for a treatment period of 6 weeks. Data reporting will be done on an electronic Case Report Form (eCRF) and an eDiary. During the 2 weeks of baseline, patients will be asked to refrain from taking any medication or supplement to relieve their constipation. After 14 days the patients will return and eligibility will be re-assessed. Patients will be trained on how to use the base unit. They will activate and ingest the capsules at home by themselves, using the base unit. Patients will be instructed to complete a simple patient eDiary each day throughout the duration of the study. After 3 weeks of treatment, the patient will attend for evaluation and to receive new capsules. A final visit will take place at the end of the 6 week treatment period. Patients will receive phone calls up to twice per week and patient compliance will be monitored during the 8 weeks of the study.

Doc No: 220CLD

Rev: 03 Date: August 26, 2016

Page 9 of 93

	Patients will be authorized to use rescue medication after 3 consecutive days without a spontaneous bowel movement. Patients will report their daily bowel movements and use of medication using the eDiary. Data about time of activation of the capsules will be automatically registered and transmitted by the base unit. Patients will be requested to ingest the capsules at a specific time of the day.
Study duration	Study duration is 8 weeks - 2 weeks of baseline - 6 weeks of treatment
Endpoints	The primary efficacy endpoint is the SBM success rate, defined as an increase from the run-in period of at least one weekly Spontaneous Bowel Movement (SBM) during at least 3 of the 6 weeks of treatment. Subjects with less than 2 weeks (with at least 5 days per week) of valid diary during the treatment period will be considered as non-evaluable. Secondary efficacy endpoints include:
	Safety endpoints include all adverse events related and unrelated to the study treatment.
Patient Population	Patients with Functional Constipation refractory to existing treatments.

Doc No: 220CLD

Rev: 03 Date: August 26, 2016

Page 10 of 93

No. of	Approximately 134 subjects
Subjects	

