17.7 Data Analysis Sets

17.7.1 Full Analysis Set (FA)

The FA analysis set will consist of all subjects who were treated with at least one Vibrant capsule. Subjects with no valid post baseline assessment will not be part of the relevant analyses.

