17.7.3 Statistical Analysis of Analysis Sets

The FA analysis set will serve as the main set for safety assessments.

The PP analysis set will serve as the main set for efficacy assessments.

The primary efficacy assessment will also be performed on the FA analysis set.

Doc No: 220CLD

Rev: 03 Date: August 26, 2016

Page 57 of 93

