17.8.5 Efficacy Analysis

The subject's success status (i.e. if the subjects achieve an increase from baseline of at least 1 weekly SBM during at least 3 out of the 6 treatment weeks) will be calculated. The success rate will be presented along with its exact binomial two sided 95% Confidence Intervals (CI).

Ease of Use will be presented in a tabular form.

Doc No: 220CLD

Rev: 03 Date: August 26, 2016

Page 58 of 93

The CSBM success rate will be analyzed in the same manner.

The change from baseline in number of weekly SBM will be modeled with an Analysis of Covariance (ANCOVA) model, with baseline weekly number of SBM and site as covariates. The adjusted means of the change from baseline will be presented along with its 95% CI.

The change from baseline in count of weekly CSBM, and in symptoms, will be analyzed with similar ANCOVA models, with their respective baseline values as covariate.

Time to occurrence of SBM after intake of the first Vibrant capsule will be assessed and presented by Kaplan-Meier curves.

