17.8.8 Handling of Missing Data

Missing value will not be imputed and will be left "as-is". For the time to first SBM analysis, subjects with no known SBM will be considered left censored.

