28. SUBJECT / STUDY DISCONTINUATION

Subjects should be removed from the study whenever considered necessary for their welfare or when the subject expresses a desire to withdraw from the study. Noncompliance with the protocol, the occurrence of a Serious Adverse Event or any medical condition that, in the opinion of the investigator, warrants discontinuation from the study for the safety of the subject, may necessitate discontinuing a subject. If a subject is discontinued, the reason must be entered on the case report form and signed by the investigator. In case of any questionable situation, the study monitor or Vibrant Ltd. personnel should be consulted. When a subject is removed from the study as a result of Serious Adverse Event, a final physical examination must be performed. Subjects removed from the study because of an adverse event will be followed-up until the adverse event has been resolved.

In the case that the occurrence of adverse events is greater than anticipated, the clinical investigation will be suspended; in such a case, a safety committee will be arranged to decide if the study could be continued. The Ethics Committee will be notified and the results of the safety committee discussions will be brought for the EC review and decision.

Doc No: 220CLD

Rev: 03 Date: August 26, 2016

Page 64 of 93

Early termination could be a result of:

1. Withdrawal of informed consent by the subject.

- 2. Patients who after inclusion develop medical diseases which may affect the function and interpretation of study results.
- 3. Serious protocol deviation.
- 4. Non-compliance with medical device administration or study procedures as determined by the sponsor.
- 5. Change in subject's condition.
- 6. Patient is Lost to follow-up.
- 7. Confirmed pregnancy.
- 8. Regulatory authorities stop the trial.

During the study, patients exiting the trial will be replaced with new patients, in order to have 120 patients at the end of the trial.

Vibrant Ltd., reserves the right to discontinue any study for administrative reasons at any time, such as, but not limited to a decision to discontinue further clinical investigation with the device, improper conduct of the study by the investigator, inability to obtain the number of subjects required by the protocol, etc. Reimbursements for reasonable expenses will be made if such an action is necessary.

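### No planned analysis counts treated subjects with fewer than two valid diary weeks as failures, so no all-treated success rate stands beside the evaluable-only one

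*Combined protocol and SAP*

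**What the plan says.** Success is an increase over the run-in of "at least one weekly Spontaneous Bowel Movement (SBM) during at least 3 of the 6 weeks of treatment" (Section 17.2.1, also Section 13.1 and the synopsis). The same three places add that subjects with "less than 2 weeks (with at least 5 days per week) of valid diary during the treatment period will be considered as non-evaluable". Section 17.2.2 repeats this rule for CSBM success.

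Section 17.7.1 puts everyone who took at least one capsule into the FA set, then adds: "Subjects with no valid post baseline assessment will not be part of the relevant analyses". Section 17.7.2 forms the PP set by removing major protocol violators from the FA set. Section 17.7.3 makes PP the main efficacy set and adds: "The primary efficacy assessment will also be performed on the FA analysis set". It names no FA analysis for CSBM success.

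Section 17.8.5 plans the success rate with an exact two-sided 95% interval and treats CSBM success likewise. On missing data, Section 17.8.8 states: "Missing value will not be imputed and will be left" as it stands. Section 17.4 aims for 120 completers and raises the number to at least 134 for 10% dropout. Under Section 28, "patients exiting the trial will be replaced with new patients, in order to have 120 patients at the end of the trial".

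**The concern.** Success needs three weeks, while evaluability needs two valid ones. A subject who leaves in the first days of treatment has no recorded route to success, yet is dropped from the rate instead of being counted as not successful. The FA repeat looks as if it should give an all-treated rate, but the exclusion sits inside the endpoint definition and appears to follow the subject into that set. No non-responder, worst-case or other sensitivity analysis restores these subjects.

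The study has one arm, so there is no control group in which the same exclusion could offset the effect, and the success rate is the main efficacy result. Section 17.4 also ties the final sample size to efficacy seen at the interim analysis. Section 17.8.4 tabulates withdrawals, so attrition is visible, but it does not enter the success rate.

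**Working it through.** **1. The plan's own figure.** Completers 120, dropout 10% (Section 17.4). 120/0.9 = 133.3, rounded up to 134, which matches. The allowance is therefore 134 - 120 = 14 dropouts.

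**2. Formula.** Let N = treated subjects, k = those with fewer than two valid diary weeks, S = successes among the rest.
- Evaluable-only rate: S/(N-k)
- All-treated rate, the k as failures: S/N
- Ratio: N/(N-k), above 1 whenever k is at least 1. The rates differ if S is also at least 1.

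For N = 134 the ratio is 134/130 = 1.03 at k = 4 and 134/120 = 1.12 at k = 14.

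**3. Assumptions.** The plan gives neither an expected success rate nor an expected k. I take S = 36, 60 and 72, which is 30%, 50% and 60% of 120 completers, and three values of k:
- k = 0: every treated subject is evaluable.
- k = 4: dropout spread evenly over 42 days. Two weeks with five diary days each cannot be reached before day 12, so about 14 x 12/42 = 4 leave too early. The other 10 leavers are evaluable and, for simplicity, contribute no successes.
- k = 14: every allowed dropout is non-evaluable. This is an upper bound for the dropout allowance.

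**4. Results.**

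| k | S | Evaluable-only | All-treated | Gap (points) |
|---|---|---|---|---|
| 0 | any | S/134 | S/134 | 0 |
| 4 | 36 | 36/130 = 27.7% | 26.9% | 0.8 |
| 4 | 60 | 60/130 = 46.2% | 44.8% | 1.4 |
| 4 | 72 | 72/130 = 55.4% | 53.7% | 1.7 |
| 14 | 36 | 36/120 = 30.0% | 26.9% | 3.1 |
| 14 | 60 | 60/120 = 50.0% | 44.8% | 5.2 |
| 14 | 72 | 72/120 = 60.0% | 53.7% | 6.3 |

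Exact 95% intervals for S = 60: 40.7-59.3 on 120, 37.4-55.1 on 130, 36.2-53.6 on 134. At n = 120 the half-width is 8.5-9.3 points over this range.

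If the 10 late leavers at k = 4 succeed as often as completers, the gap hardly changes: 65/130 = 50.0% against 65/134 = 48.5%, or 1.5 points.

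**5. PP set.** Removing violators can reverse the order. With k = 4 and S = 60, drop 10 violators of whom 7 were successes: 53/120 = 44.2%, below 60/134 = 44.8%.

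**6. Against the unknown true rate.** With 60/120 reported and 14 excluded, suppose r of the 14 would have succeeded. The all-treated rate is then 44.8% (r = 0), 49.3% (r = 6), 50.0% (r = 7), 50.7% (r = 8) or 55.2% (r = 14). The reported 50.0% is too high up to r = 6, exact at 7 and too low from 8.

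**The case against.** The exclusion is prespecified and openly stated, the study is a pilot (Section 15.1) that is mainly descriptive (Section 17.8.2.1), and no success threshold exists. At the more plausible k = 4 the gap is small beside the interval half-width. The calls and next-day contact about missed diary entries (Section 15.9) may keep k lower still. A reader given the success count and the FA size could work out S/N. All of this stands, and it limits the weight of the point. It does not supply the missing analysis.

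Removal from the FA repeat is also inferred. Section 17.7.1 drops only subjects without any valid post-baseline assessment, and someone with one valid week arguably has one. How that sentence combines with the endpoint rule is not stated. But nothing in the plan counts such a subject as a failure.

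Some stronger readings are tempting, and the documents do not support them:
- *All early leavers vanish.* A leaver on days 12-14 can have two valid weeks, is then evaluable, and counts as a failure.
- *Replaced patients drop out of the FA set.* Taking one capsule defines membership, so they stay in it. What Section 28 leaves open is how they enter the success rate.
- *CSBM success has no FA analysis.* Section 17.8.5 arguably carries the repeat over, while Section 17.7.3 names only the primary endpoint. The matter is open.

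**Conclusion.** The gap in the plan is real and modest in size. The evaluable-only FA rate equals the all-treated rate with non-evaluable subjects as failures when there are none, and exceeds it by N/(N-k) once there is at least one such subject and at least one success. Under the assumptions of 134 treated and 30-60% success, that is about 0.8-1.7 points for k = 4 and at most 3.1-6.3 points if the whole dropout allowance is non-evaluable. This rests on reading the endpoint rule as applying in the FA repeat.

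A reader might infer that the main PP rate is certainly inflated, or that the true success rate is certainly overstated. Neither follows. PP also drops major violators, and the direction against the true rate depends on how many excluded subjects would have succeeded; it is likely upward if diary loss goes with non-response. Nor is this a type I error problem: Section 17.3.3 bases no inference on the primary endpoint. The consequence is a possibly optimistic estimate and interval.

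**What to change.** In Sections 17.7.3 and 17.8.5, mirrored in the statistical part of the synopsis, add one FA analysis of SBM success and the same for CSBM success:
- The denominator is every subject who took at least one capsule, including those replaced under Section 28.
- Subjects with fewer than two valid diary weeks count as failures. State that this holds for the added analysis despite the exclusions in Sections 17.2.1, 17.2.2 and 17.7.1 and the no-imputation rule in Section 17.8.8.
- Report how many such subjects there are, and show the rate with its exact 95% interval beside the planned PP and evaluable-only FA rates.

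The endpoint wording and the planned rates stay unchanged. The cost is a short amendment to the analysis text under Section 26, with no new data, visits or subjects. The downside is a rate equal to or slightly below the evaluable-only FA rate, and a conservative handling of subjects who stayed on treatment but did not keep the diary.

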17.2.2 Secondary Efficacy Endpoints

Secondary efficacy endpoints include:

- Ease of use
- CSBM success rate, defined as as an increase from the run-in period of at least one weekly Complete Spontaneous Bowel Movement (CSBM) during at least 3 of the 6 weeks of treatment. Subjects with less than 2 weeks (with at least 5 days per week) of valid diary during the treatment period will be considered as non-evaluable.
- Change from baseline in weekly number of Spontaneous Bowel Movement (SBM).
- Change from baseline in weekly number of Complete Spontaneous Bowel Movement (CSBM).
- Change from baseline in average stool consistency, using the Bristol Stool Scale
- Change from baseline in average bloating.
- Change from baseline in average abdominal gas.
- Change from baseline in average abdominal pain.
- Change from baseline in average straining.
- Change from baseline in abdominal discomfort.
- Change from baseline in average abdominal pain during defecation.
- Time to occurrence of spontaneous bowel movement after capsule.

17.2.3 Safety Endpoints

Safety endpoints include all adverse events related and unrelated to the study treatment.

17.3 Interim Analyses

One (1) interim analysis is planned, after approximately 20 subjects will complete the 6 weeks of treatment with the Vibrant capsule.

17.3.1 Procedure

At the interim analysis, after all the relevant data will be entered into the database, and the database cleaned, a soft lock to the database will be performed. The ease of use, tolerability and safety will be assessed.

17.3.2 Decision Rules

The following decision upon the interim analysis report are planned:

- O Stop the study in case of severe safety concern
- o Continue the study as planned.
- o Modify the frequency of use and/or the device's usability

Doc No: 220CLD

Rev: 03 Date: August 26, 2016

Page 56 of 93

17.3.3 Controlling the Alpha level for the primary endpoint

As the interim analyses is planned, only for futility or to modify the frequency of use and/or the device's usability, and that the primary endpoint is not based upon any statistical inference, not at the interim (only point estimate will be calculated) and not end the final analyses, no procedure is requested to control the overall alpha level.

17.4 Sample size

The chosen sample size is 120 subjects who will be enrolled and complete the 6 treatment weeks.

The final sample size will be determined following the completion of the interim analysis, based on the efficacy of the new frequency of vibration capsule.

The sample size account for a potential 10% of drop-outs.

The sample size will be increased to at least 134 to account for a potential 10% of dropouts, as needed.

17.5 Randomization

This is an open-label, single-arm study.

17.6 Blinding

Not Relevant.

17.7 Data Analysis Sets

17.7.1 Full Analysis Set (FA)

The FA analysis set will consist of all subjects who were treated with at least one Vibrant capsule. Subjects with no valid post baseline assessment will not be part of the relevant analyses.

17.7.2 Per-Protocol (PP)

The per-protocol analysis set will consist of all subjects from the FA analysis set without major protocol violations.

17.7.3 Statistical Analysis of Analysis Sets

The FA analysis set will serve as the main set for safety assessments.

The PP analysis set will serve as the main set for efficacy assessments.

The primary efficacy assessment will also be performed on the FA analysis set.

Doc No: 220CLD

Rev: 03 Date: August 26, 2016

Page 57 of 93

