15.13 Prohibited medication

The medications listed below will be prohibited during the entire study:

- Medications that may affect intestinal motility
- Prokinetics
- Antidepressants
- Anti-Parkinsonian medications
- Opiates
- Opioids
- Calcium-channel blockers
- Aluminum/magnesium hydroxide.

Chronic use of non-steroidal anti-inflammatory drugs (NSAIDs) is also prohibited. Chronic use is defined as taking full dose NSAIDs on a regular basis (i.e. more than three times a week) for at least six months.

Patients on cardiac doses of aspirin may be enrolled in the study.

The following medications are equally prohibited, but with an exception when the subject has been on a stable dose of the medication for at least 3 months:

- Antidepressants
- Thyroid or hormonal replacement therapy.

Doc No: 220CLD

Rev: 03 Date: August 26, 2016

Page 48 of 93

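### Only the primary efficacy endpoint is repeated on the FA set, so any effect of PP exclusions on the secondary efficacy endpoints would not be shown

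*Combined protocol and SAP*

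**What the plan says.** Section 17.7.3 assigns the analysis sets. FA is the main set for safety. For efficacy, "The PP analysis set will serve as the main set for efficacy assessments", followed by one addition: "The primary efficacy assessment will also be performed on the FA analysis set". Section 17.7.1 defines FA: "The FA analysis set will consist of all subjects who were treated with at least one Vibrant capsule"; subjects with no valid post-baseline assessment drop out of the analyses concerned. Section 17.7.2 defines PP as "all subjects from the FA analysis set without major protocol violations", and no list or grading of major violations appears in the text available.

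Section 17.2.2 lists the secondary efficacy endpoints. Section 17.8.5 gives their methods: an exact interval for CSBM success, ANCOVA for the changes from baseline and Kaplan-Meier for time to SBM. It names no analysis set for any of them. Section 17.8.1 places only baseline characteristics and safety on all enrolled subjects. Section 17.8.8 rules out imputation.

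**The concern.** The study has no control arm, and 17.3.3 says that "the primary endpoint is not based upon any statistical inference". What it delivers is a set of estimates, so the choice of subjects behind each estimate matters.

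PP exclusions here can be tied to outcome. Section 15.9 asks patients to refrain from constipation medication, and 15.10 allows rescue only after three days without an SBM. A patient who is not helped may take a laxative outside those rules, be classed as a violator and leave PP as a failure. Section 28 leaves non-compliance to the sponsor's determination, treatment is unblinded, and 15.7 has diary data reaching the eCRF every day. Exclusions of this kind would raise the PP estimates.

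The opposite is also possible. Section 15.13 prohibits, among others, "Medications that may affect intestinal motility". If users of such drugs were classed as major violators, removing them could take out false successes and lower the estimates.

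For the SBM success rate, a reader can compare PP with FA and see the net effect. For the secondary endpoints, a reader would have the PP figure alone.

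**Working it through.** **Which set applies to the secondary endpoints.** Section 17.8.5 names no set, so 17.7.3 governs, and its FA repeat covers the primary assessment only. The sentence "The CSBM success rate will be analyzed in the same manner" in 17.8.5 follows the description of the rate and its exact interval, so it most naturally refers to the method. Even if it carried the analysis set along, it would cover CSBM success and no other endpoint. No other section puts a secondary efficacy endpoint on FA.

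**The plan's own figure.** Section 17.4 has 120 completers and 10% drop-out: 120 / (1 - 0.10) = 133.3, rounded up to 134. This matches the plan. The point does not depend on it.

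**Size of an unseen shift, success rates.** The documents give no exclusion rate and no success rate, so these inputs are assumptions: 120 evaluable FA subjects (120 is the completer target in 17.4; FA itself could be larger), S successes, k subjects removed, j of them failures.

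PP rate = (S - (k - j)) / (120 - k)

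| FA rate | k | j | PP rate | PP minus FA (points) |
|---|---|---|---|---|
| 60/120 = 50% | 12 | 12 | 60/108 = 55.6% | +5.6 |
| | 12 | 9 | 57/108 = 52.8% | +2.8 |
| | 12 | 6 | 54/108 = 50.0% | 0 |
| | 12 | 4 | 52/108 = 48.1% | -1.9 |
| | 6 | 6 | 60/114 = 52.6% | +2.6 |
| | 6 | 2 | 56/114 = 49.1% | -0.9 |
| 36/120 = 30% | 12 | 12 | 36/108 = 33.3% | +3.3 |
| | 12 | 9 | 33/108 = 30.6% | +0.6 |
| | 12 | 6 | 30/108 = 27.8% | -2.2 |
| | 12 | 4 | 28/108 = 25.9% | -4.1 |
| | 6 | 6 | 36/114 = 31.6% | +1.6 |
| | 6 | 2 | 32/114 = 28.1% | -1.9 |

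For scale, the exact 95% CI is 40.7% to 59.3% for 60/120 (half-width 9.3 points) and 22.0% to 39.0% for 36/120 (half-width 8.5 points).

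**Mean-change endpoints.** Let r be the share removed and d the mean of the kept subjects minus the mean of the removed subjects. The FA mean is (1 - r) × kept + r × removed, so PP - FA = r × d. With r = 0.10, the shift is +0.10 SD for d = 1 SD, +0.05 SD for d = 0.5 SD and -0.05 SD for d = -0.5 SD. The 95% CI half-width at n = 120 is t(0.975, 119) / √120 = 0.18 SD.

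**A more extreme case.** With FA n = 134 and 27 subjects (20%) removed, none of them a success, 43/107 = 40.2% on PP becomes 43/134 = 32.1% on FA (gap 8.1 points; FA half-width 8.2). In the same way, 54/107 = 50.5% becomes 54/134 = 40.3% (gap 10.2; FA half-width 8.6). Here the shift reaches or passes the half-width, but nothing in the documents supports either a 20% exclusion rate or an absence of successes among those removed.

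**The case against.** The strongest case on the other side is that little depends on these tables. Section 15.1 calls the study a pilot, 17.8.2.1 calls the analyses mainly descriptive, 17.8.1 makes any p-values nominal, and no decision rule uses a secondary endpoint. This stands, and it keeps the point to a cheap improvement.

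It can also be said that the primary endpoint's PP-FA gap gives a hint about CSBM success and weekly SBM, which come from the same subjects and diary, and that 17.8.4 reports non-completion. That is partly right. It is indirect evidence, since complete movements and symptom scores can respond differently to the same exclusions.

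The repeat also recovers only part of the selection. Subjects with too few valid diary weeks are non-evaluable for CSBM success on either set (17.2.2), and those with no valid post-baseline assessment leave the FA analyses too (17.7.1). This stands. The prohibited-drug route is narrow as well: 15.10 already disqualifies movements within 24 hours of a laxative, on both sets, and 15.13 does not say that use of a prohibited drug is a major violation.

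A reader might infer more than the documents support:

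- That a PP lead hides or inflates the primary result. Both primary rates are reported, so only their order is at issue.
- That PP must favour the device. The sign is open, as the table shows.
- That ease of use is caught as well, because 17.2.2 lists it. Sections 12 and 17.1 name it separately from efficacy and 17.3.1 groups it with tolerability and safety, so that reading is weak.

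**Conclusion.** The point holds for the secondary efficacy endpoints other than ease of use. As written, the plan produces PP estimates only, and a shift caused by excluding major violators would not be shown. Section 17.7.3 does not forbid further FA tables, but none is planned.

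The likely size is modest. With 5 to 10% removed and FA success of 30% or 50%, the scenarios run from -4.1 to +5.6 points, and the mean-change shifts from -0.05 to +0.10 SD. All are inside the 95% CI half-width. They would still be bias, which the interval does not reflect. Every input to these figures is assumed, and a much higher exclusion rate among non-responders would give more. The study is not invalidated and no type I error question arises.

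**What to change.** Extend the last sentence of 17.7.3 so that the FA repeat covers the secondary as well as the primary efficacy assessments. Preferably let FA lead for the secondary endpoints, with PP as the supportive analysis. The order for the primary endpoint can stay, since both rates are reported.

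As an accompanying clarification in 17.7.2, state what counts as a major violation and require the classification to be complete before database lock.

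The cost is the wording of two sections and a few extra tables, with no new data. The downside is that some reported estimates may be slightly less favourable. The change does not address non-evaluable subjects, subjects with no valid post-baseline assessment or the absence of imputation in 17.8.8.
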